6.5 Treatment Compliance

Study drugs will be administered or dispensed only to eligible patients under the supervision of the investigator or identified sub-investigator(s). The appropriate study personnel will maintain records of study drug receipt and dispensing.

6.6 Drug Accountability

Study drugs should be kept in a secure place and must be administered only to patients in the trial. A log of study drug (received, administered to patients and destroyed) must be maintained and signed by the person responsible for drug handling at each center. Study site/institution personnel will record all study drug administered during this trial on the drug-dispensing log. Description of monitoring of the overall drug accountability will be detailed in study and site specific procedures.

The nuclear medicine specialist or radiation oncologist at the center is responsible for drug accountability for radium-223. When the drug accountability has been monitored, the vials can be destroyed in accordance with hospital procedure for the handling of radioactive material, normally after storage for 4 months from date of receipt (>10 half-lives) before disposal; they may then be disposed as non-radioactive waste.

6.7 Follow-Up Procedures

6.7.1 Blood Draws

Subsequent to randomization, patients will be followed clinically and radiographically. A detailed medical and physical examination with blood draws for PSA, LDH, CBC w/Diff, Serum Chemistry panel (CMP), ctDNA (CAPP-seq), immune cell profiling (ImmunoSEQ), CTCs (EPIC HD-CTC), immunophenotyping, and testosterone will be performed within the first month, months 3, 6 and 12 (from date of randomization) for all patients. Correlatives at outside sites are optional and not mandatory. In-clinic visits are not required otherwise, unless indicated by laboratory tests. For men randomized to the SABR + Radium-223, they will also receive monthly CBCs as per standard of care for radium-223 infusions (within 7-10 days of radium-223 injection). Following 12-months patients will be followed by any physician as per standard of care which may include but not be limited to every 3-6 month clinic visits, laboratory evaluations for PSA and imaging, if appropriate. Further labs and imaging is at the discretion of the treating physician. This information of two year followup will be collected by the clinical study team for all participating sites.

Correlative science blood draws will be performed as above (details for these blood draws are contained within the APPENDIX III-V).

Briefly:

CAPP-Seq: 30-ml whole blood in purple top (EDTA) tubes (see APPENDIX III for details). The blood is stored in a freezer, then shipped in batches as per APPENDIX III. Baseline, months 3, 6 and 12 from randomization for both arms.

EPIC HD-CTC: 4-10 ml Streck Cell-Free DNA BCT tubes (see APPENDIX IV for details). Whole blood is shipped out the same day as it is drawn as per APPENDIX IV. Baseline and day 180 from all men.

ImmunoSEQ: 10-ml whole blood in purple top (EDTA) tubes (see APPENDIX V for details). The patient samples are stored in a 80 Degree Celsius freezer and shipped in batches as per APPENDIX V. Baseline and day 90 from all men.

Immunophenotyping: 2-10-mL whole blood in green top (heparin) tubes (see APPENDIX VIII for details).

Only participating sites that have the resources to do so, will participate in blood draw collection and shipment.

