Radium-223 is a ready-to-use solution and should not be diluted or mixed with any solutions. Each vial is for single use only. Parenteral drug products should be inspected visually for particulate matter and discoloration prior to administration, whenever solution and container permit.

Before the first administration of Xofigo, the absolute neutrophil count (ANC) should be $\geq 1.5 \times 10^9/L$, the platelet count $\geq 100 \times 10^9/L$ and hemoglobin $\geq 10 \text{ g/dL}$. Before subsequent administrations of Xofigo, the ANC should be $\geq 1 \times 10^9/L$ and the platelet count $\geq 50 \times 10^9/L$. If ANC is not within normal limit prior to protocol window, then CBC can be drawn, per treating physician advisement. All doses 6 doses should still be administered regardless of

treatment delay due to ANC. Unless, there is no recovery to these values within 6 to 8 weeks after the last administration of Xofigo, despite receiving supportive care, then further treatment with Xofigo should be discontinued. Patients with evidence of compromised bone marrow reserve should be monitored closely and provided with supportive care measures when clinically indicated. Discontinue Xofigo in patients who experience life-threatening complications despite supportive care for bone marrow failure.

Dosage:

The dose regimen of radium-223 is 50 kBq (1.35 microcurie) (55 kBq/kg (1.49 microcurie/kg) after implementation of the NIST update) per kg body weight, given at 4 week intervals for 6 injections.

The volume to be administered to a given patient should be calculated using the:

- Patient's body weight (kg)
- Dosage level 50 kBq/kg body weight (55 kBq/kg after implementation of the NIST update) or 1.35 microcurie/kg body weight (1.49 microcurie after implementation of the NIST update)
- Radioactivity concentration of the product (1,000 kBq/mL; 27 microcurie/mL (1,100 kBq/mL after implementation of the NIST update; 29.7 microcurie/mL) at the reference date
- Decay correction factor to correct for physical decay of radium-223.

The total amount (volume to be drawn into the syringe) to be administered to a patient should be calculated as follows:

Volume to be administered (mL) =
Body weight (kg) x dose (50 kBq/kg b.w)^a/
DK factor x 1,000 kBq (0.027 mCi)/mL^b

^a 55 kBq/kg after implantation of the NIST update

^b 1,100 kBq (29.7 microcurie)/mL after implantation of the NIST update

Decay Correction Factor Table

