J.	For patients to receive Xofigo infusion #1, the following criteria must be met: 
 • ANC $\geq 1.5 \times 10^3 / \text{L}$ • Platelets $\geq 100 \times 10^3 / \text{L}$ • Hemoglobin $\geq 10 \text{ g / dL}$ For patients to receive Xofigo infusions #2-6, the following criteria must be met: 
 • ANC $\geq 1 \times 10^3 / \text{L}$ • Platelets $\geq 50 \times 10^3 / \text{L}$ If a patient fails to meet the criteria, the criteria should be re-checked every 7-10 days. If the patient does not recover to the required values within 6-8 weeks, further Xofigo treatments should be discontinued.
K.	CT/MRI or Axumin/Choline PETs should be used to measure tumor dimensions at baseline and to measure tumor dimensions and evaluate radiographic response on day 181 and on day 361. Imaging used at baseline can be further used at Day 180 and Day 360, respectively.
L.	Instructions for CAPP-Seq Sample Collection & Processing can be found in Appendix III of the protocol.
M.	Instructions for EPIC-HD CTC Sample Collection & Processing can be found in Appendix IV of the protocol.
N.	Instructions for ImmunoSeq Sample Collection & Processing can be found in Appendix V of the protocol.
O.	Instructions for Immunophenotyping Sample Collection & Processing can be found in Appendix VIII of the protocol. Only applicable to JHU/JHSOM. Outside sites will not be performing Immunophenotyping.
P.	Instructions for Invitae Saliva Kit Sample Collection can be found in Appendix VII of the protocol.
Q.	Instructions for Rectal Swab Collection for Microbiome Analysis can be found in Appendix VI of the protocol.
R.	Instructions for SBRT/SABR treatment planning can be found in section 6.3 of the protocol.
S.	Instructions and information for Xofigo (Radium-223) can be found in section 6.3 of the protocol.
T.	After randomization, only interval concomitant medications, interval medical history, and limited physical exam information needs to be collected only once, either during Day 1 visit or during SABR.
U.	Per SOC, patient's will have a PSMA PET/CT prior to enrollment/randomization. Patients who are still enrolled in the trial will have a PSMA PET/CT 360 Days from initial PSMA PET/CT (see V).
V.	ONLY for sites participating in PSMA PET-CT - If applicable, patient's will have a PSMA PET/CT 12 Months from the first completed PSMA PET ("approximately 13/14 months from randomization")

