10.5 Reporting Procedures

10.5.1 General and Multi-Site Reporting

10.5.1.1 General

Adverse events will be recorded at each visit. If an adverse event requiring medical attention occurs between visits, this will be recorded as well. The variables to be recorded for each adverse event include, but are not limited to, onset, resolution, intensity, action taken, outcome, causality rating and whether it constitutes an SAE or not. The intensity of the adverse event should be captured using CTCAE criteria, version 4.0, when possible. Additionally, the collection of all skeletal related events will be collected for 2 years.

All Serious Adverse Events (SAEs) will be reported via the AdEERS (Adverse Event Expedited Reporting System) application accessed via the CTEP web site
([https://webapps.ctep.nci.nih.gov/openapps/plsql/gadeers_main\\$.startup](https://webapps.ctep.nci.nih.gov/openapps/plsql/gadeers_main$.startup)).

In addition, any safety concerns, new information that might affect either the ethical and or scientific conduct of the trial, or protocol deviations will be immediately reported to the industry collaborator Bayer HealthCare Pharmaceutical Inc. When required, and according to local law and regulations, serious adverse events must be reported to the Ethics Committee and Regulatory Authorities. All serious adverse events should be reported to Bayer HealthCare Pharmaceutical Inc. within 24 hours.

All adverse events will be captured on the appropriate study-specific case report forms (CRFs).

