14.1.2 Secondary Objectives

- To describe the toxicity of SABR and SABR + Radium-223 delivered for the population enrolled using grading with CTCAE v. 4.0
- To determine local control at 12-months after SABR and SABR + Radium-223 in patients with oligometastatic disease.

- To assess time to locoregional progression, time to distant progression, time to new metastasis and duration of response after randomization to SABR *versus* SABR + Radium-223.
- To assess ADT-free survival (ADT-FS) of this patient population after randomization defined as the time interval between the day of randomization and the initiation of ADT. ADT will typically be initiated on progression and/or development of new metastases.
- To assess quality of life following SABR *versus* SABR + Radium-223 arms. Brief Pain Inventory form which will be filled out by the patient at the treatment response intervals outlined above.

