14.5 Analysis of Secondary Objectives

- For safety analysis, adverse events will be summarized by type and grade.
- Kaplan-Meier (KM) estimates will be used to summarize ADT-free survival (ADT-FS), time to locoregional progression (TTLP), time to distant progression (TTDP), time to new metastasis (TNM) and duration of response over time. The median PFS, ADT-FS, TTLP, TTDP TNM and duration of response will be reported.
- The efficacy of SABR + Radium-223 in men with oligometastatic disease will also be determined by measuring local control of each lesion at 12-months.

Each metastatic lesion will be considered a target lesion and independently evaluated for response using RECIST 1.1 or bone scan evaluation criteria above. The lesion will be coded as being locally controlled if it is considered stable radiographic disease or if there is evidence of a partial or complete response. Local control assessment will start at three months following randomization and continuous assessment will be pursued during the follow-up period. The proportion of the lesions that have a stable or better response will be estimated using generalized estimating equation.

- Quality of life will be assessed using the Brief Pain Inventory form. An overall score will be calculated pre-treatment and at the time of the 2nd radiologic reassessment. The change in score will be evaluated with a paired t-test.

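### In months 0–6 the radium arm has about three times as many scheduled post-treatment blood counts as the SABR arm, and section 14.5 makes no allowance for this if toxicity is read by arm

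*Combined protocol and SAP*

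**What the plan says.** **Schedule.** Under section 6.7.1, the examination and blood draws, which include the CBC, "will be performed within the first month, months 3, 6 and 12 (from date of randomization) for all patients". The section adds: "In-clinic visits are not required otherwise, unless indicated by laboratory tests". For men on SABR + Radium-223, "they will also receive monthly CBCs as per standard of care for radium-223 infusions". Section 6.4 has radium-223 "given at 4 week intervals for 6 injections". Footnote I of the radium calendar (section 8) requires a CBC before each infusion. Footnote J says that if the dosing counts are not met, "the criteria should be re-checked every 7-10 days". No such rule applies to the SABR arm.

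**Recording.** Section 10.5.1.1: "Adverse events will be recorded at each visit". Events between visits that need medical attention are recorded too. Section 10.2.1 treats an abnormal laboratory value as an AE only when it produces symptoms or leads to treatment or more testing. Section 10.3 lists falls in neutrophils and platelets among the effects to look for.

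**Analysis.** The objective in section 14.1.2 is "To describe the toxicity of SABR and SABR + Radium-223 delivered for the population enrolled". The analysis in section 14.5 is: "For safety analysis, adverse events will be summarized by type and grade". Section 14.6 adds only who is evaluable. Section 14 sets no common time points and no allowance for the difference in monitoring.

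**The concern.** An event that is looked for more often is found more often. Short falls in blood counts are usually silent, so their detection depends on when blood is drawn. Low blood counts are also a toxicity that the protocol itself watches for with radium-223. If AEs are set out by arm, which is the natural display in a randomized trial whose objective names both treatments, a higher frequency in the radium arm will mix true excess with closer observation. The extra visits may also bring out more non-laboratory complaints.

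At stake is how much toxicity readers attribute to radium-223 in an open-label trial of 32 men per arm, where a descriptive table will carry most of the safety message.

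**Working it through.** The plan gives no detection figure, so there is none of its own to reproduce.

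**Step 1. Count the draws to day 181.**
- Infusions are every 4 weeks, six in all: days 1, 29, 57, 85, 113 and 141. The count before infusion 1 is pre-treatment and is left out.
- Radium arm: days 29, 57, 85, 113 and 141 plus the shared draws near days 91 and 181, so 7; or 6 if days 85 and 91 are one draw.
- SABR arm: days 91 and 181, so 2; or 3 if the first-month draw is after treatment (taken here as day 31).
- Two draws is the likelier reading. Section 6.2 places Day 1 within 30 days of randomization. The calendar footnotes put Day 1 research blood before treatment and let recent pre-study labs stand in for Day 1 labs. The next shared case report forms in section 12.1 are for Day 90.
- Ratio of counts: 6/2 = 3.0 to 7/2 = 3.5; with three SABR draws, 6/3 = 2.0 to 7/3 = 2.3.

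**Step 2. Share of episodes detected, with equal true rates.** Assume onset uniform over days 0–181 and a fixed duration of d days. An episode is caught if a draw at day x falls within it, that is, if onset lies in [x − d, x]. The share caught is the total length of these intervals, overlaps counted once, divided by 181.

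Example, d = 14. SABR: 2 × 14 = 28, and 28/181 = 15.5%. Radium: five separate draws give 5 × 14 = 70, days 85 and 91 together cover 20, and 90/181 = 49.7%. Ratio 90/28 = 3.21.

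| d (days) | Radium, 7 draws | SABR, 2 draws | Ratio | SABR, 3 draws | Ratio |
|---|---|---|---|---|---|
| 7 | 48/181 = 26.5% | 14/181 = 7.7% | 3.43 | 21/181 = 11.6% | 2.29 |
| 14 | 90/181 = 49.7% | 28/181 = 15.5% | 3.21 | 42/181 = 23.2% | 2.14 |
| 28 | 168/181 = 92.8% | 56/181 = 30.9% | 3.00 | 84/181 = 46.4% | 2.00 |
| 42 | 100% | 84/181 = 46.4% | 2.15 | 115/181 = 63.5% | 1.57 |
| 60 | 100% | 120/181 = 66.3% | 1.51 | 151/181 = 83.4% | 1.20 |
| 90 | 100% | 180/181 = 99.4% | 1.01 | 100% | 1.00 |

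**Step 3. Vary the assumptions** (three-SABR-draw values in parentheses).
- Days 85 and 91 as one draw: 3.0 (2.0) for durations up to 28 days.
- Radium counts about 8.5 days before infusions 2–6, in line with the 7–10 day window in section 6.7.1: 3.46 at 14 days and 2.86 at 28 days (2.31 and 1.90).
- Window extended to day 361 with the shared month-12 draw: 2.62 at 7 days and 2.33 at 28 days (1.96 and 1.75).
- The radium calendar also has mid-cycle columns whose cells cannot be read. If those were CBC draws, the 14-day ratio would be about 6 (4). I do not rely on this.

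**Step 4. Per man.** With a chance p of a low count at each draw, and draws taken as independent, the chance of at least one in k draws is 1 − (1 − p)^k. For 7 versus 2 draws:
- p = 5%: 30.2% versus 9.8%, ratio 3.1; in 32 men per arm, 9.7 versus 3.1 men.
- p = 10%: 52.2% versus 19.0%, ratio 2.75.
- p = 20%: 79.0% versus 36.0%, ratio 2.2.

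**Step 5. From low count to AE.** Under section 10.2.1 a silent low count that leads to nothing is not an AE in either arm. A radium-arm count that fails the dosing criteria must be repeated under footnote J, and a repeat count can be read as further testing. The same silent low count in the SABR arm has no mandated repeat. Section 10.3 meanwhile asks for attention to neutrophil and platelet falls without this condition. The three places do not settle which low counts become AEs.

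**The case against.** A reader might infer that the AE table will show three times as many cytopenias in the radium arm. The documents do not support that. The ratios above concern detection of low counts, and section 10.2.1 keeps many of these out of the AE table in both arms. Section 14.5 does not state a by-arm table or a test. Section 14.1.2 describes the toxicity of both treatments without setting one against the other, and the synopsis and section 3.3 name only SABR + Radium-223. A by-arm reading is a fair inference, not a stated plan.

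The size also depends on duration. Footnote J allows 6 to 8 weeks for recovery. At 42 days the ratio is 2.15, and at 56 days 181/112 = 1.6. Month 12 dilutes it further, and AEs are collected for two years.

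Other points carry weight. The extra counts are described as standard of care with radium-223. Whether the calendar schedules AE evaluation at infusion visits cannot be read, so that part rests on section 10.5.1.1. Events that bring a man to medical attention are recorded in either arm and should be less affected.

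A further tempting step is to say that the imbalance distorts the safety stopping rule. It does not: section 14.3 monitors the radium arm alone against a fixed 20%.

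What remains is that monitoring is unequal, that the re-check rule can make the AE definition work differently in the two arms, and that section 14 is silent on both.

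**Conclusion.** The concern holds in a limited form. In the first six months, short low-count episodes can be detected up to about three times as often in the radium arm with no true difference. With two SABR draws the range is about 1.5–3.5 for episodes up to 60 days; with three it is about 1.2–2.3. The imbalance disappears near 90 days.

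These figures assume uniform onset, fixed duration, equal true rates and full adherence to the schedule. Episode durations are not given in the documents. The effect on recorded AEs will be smaller by an amount the documents do not allow one to compute. The primary endpoint is not touched by this point. It is worth correcting because any by-arm reading of the toxicity results would otherwise mix detection with true excess.

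**What to change.** In section 14.5:
- Keep the full AE summary by type and grade.
- Add a by-arm table of laboratory values graded by CTCAE at the draws both arms share (first month, months 3, 6 and 12), and of clinical AEs elicited at those shared visits. State whether the first-month draw is before or after treatment.
- Label findings from infusion-visit counts as radium-arm only.
- Report both tables together whenever toxicity added by radium-223 is described.

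Also reconcile footnote J, section 10.2.1 and section 10.3 on which low counts are recorded as AEs, so that the same count is handled alike in both arms.

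The cost is one more table from data already collected, plus a clarification of recording rules; no visit, draw or treatment changes. With equal true rates and equal adherence, the expected ratio in the shared-draw table is 1.0 by construction. Its drawback is low sensitivity: draws at days 91 and 181 catch only 15.5% of 14-day and 30.9% of 28-day episodes arising by day 181. Resting conclusions on that table alone could hide real transient toxicity from radium-223, so it must supplement the full summary and not replace it.

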6.7.2 Imaging

Bone scan and CT/MRI of metastatic site(s) will be at 6- and 12-months for all patients, unless indicated more frequently by clinical or laboratory findings.

If applicable, bone scan and ¹⁸F-DCFPyL (“PyL”) -PET/CT of metastatic site(s) will be at 6 months for all patients, unless indicated more frequently by clinical or laboratory findings. The results of the ¹⁸F-DCFPyL (“PyL”) -PET/CT will be made available to the treating physicians prior to enrollment to determine treatment.

The CT portion of the ¹⁸F-DCFPyL (“PyL”) -PET/CT scans at 6 months will be used to determine radiographic response based on RECIST 1.1 criteria for soft tissue lesions. Similarly, the CT or MRI scans at 6- and 12-months will be used to determine radiographic response based on RECIST 1.1 criteria for soft tissue lesions.

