PROCEDURES	
 1. Physical exam 2. CT/MRI and Bone scan and/or ¹⁸F-DCFPyL (“PyL”) PET/CT of Involved Site 3. Randomization 4. Blood draws, Rectal Swab and Invitae Test 5. SABR versus SABR + Radium-223 6. CT/MRI Scan and Bone Scan or Axumin/Choline-PET of Involved Site at 6 months 8. ¹⁸F-DCFPyL (“PyL”) PET/CT at 360 Days from first “PyL”

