4.4 Rationale for Radium-223 for Bone Metastases in Prostate Cancer

Radium-223 is an alpha-emitting radioisotope which is a bone-seeking calcium mimetic. It selectively targets the area with increased bone turnover, especially within the microenvironment of osteoblastic or sclerotic metastases. It has been approved by FDA for the treatment of metastatic castrate-resistant prostate cancer (mCRPC) with symptomatic bone metastases and without known visceral disease based on its ability to extend overall survival as shown its pivotal phase III trial. Unlike beta particle emitting radiopharmaceuticals, radium-223 emits high-energy alpha particles of short range (<100 μ m) thus saving the surrounding healthy tissues and significantly reducing unwanted myelotoxicity.

Radium-223 was approved by the US FDA on May 15, 2013 based on the interim results from a Phase III randomized trial, the ALSYMPCA study (Alpharadin in the treatment of patients with symptomatic bone metastases in castration-resistant prostate cancer). In this trial, 921 patients who had received, were not eligible to receive, or declined docetaxel were randomly assigned in a 2:1 ratio to receive six injections of radium-223 (at a dose of 50 kBq per kilogram of body weight intravenously (55 kBq/kg after implementation of NIST standard update) every 4 weeks or matching placebo. At the interim analysis, which involved 809 patients, radium-223, as compared with placebo, significantly improved overall survival (median, 14.0 months vs. 11.2 months; HR=0.70; 95% CI, 0.55 to 0.88; two-sided P=0.002). The updated analysis involving 921 patients confirmed the radium-223 survival benefit (median, 14.9 months vs. 11.3 months; HR=0.70; 95% CI, 0.58 to 0.83; P<0.001). The rate of AEs was consistently lower in the radium-223 group than in the placebo group for all AEs (93% vs. 96%), grade 3 or 4 AEs (56% vs. 62%), and serious AEs (47% vs. 60%). There were no clinically meaningful differences in the frequency

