9.5 Response Criteria

9.5.1 Evaluation of Target Lesions/PSA Response

Complete Response (CR): Disappearance of all target lesions and PSA $<$ pre-SBRT PSA

Partial Response (PR): At least a 30% decrease in the sum of the longest diameter (LD) of target lesions, taking as reference the baseline sum LD. Or a third of the lesions are negative or no change by bone scan and PSA \leq pre-SBRT PSA.

Progressive Disease (PD): At least a 20% increase in the sum of the LD of target lesions, taking as reference the smallest sum LD recorded since the treatment started or the appearance of ≥ 1 new lesion(s). Or ≥ 1 new lesion(s) appear by bone scan. Or PSA $\geq 25\%$ increase in PSA from nadir or > 50 ng/ml.

Stable Disease (SD): Neither sufficient shrinkage to qualify for PR nor sufficient increase to qualify for PD, taking as

reference the smallest sum LD since the treatment started. Or PSA \geq pre-SBRT PSA, but not $\geq 25\%$ increase in PSA from nadir and <50 ng/ml.

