9.5.5 Clinical Response Parameters

Progression is a composite endpoint defined from the Prostate Cancer Working Group 2 (PCWG2) criteria for metastatic castrate resistant prostate cancer (mCRPC) (75) and our previous trials in a population of men with biochemical failure without metastases (72-74). Progression will be defined as either: 1) a $\geq 25\%$ increase in PSA from nadir (and by ≥ 2 ng/mL), requiring confirmation ≥ 4 weeks later (PCWG2 criteria); and/or, 2) clinical/radiographic-progression defined as symptomatic progression (worsening disease-related symptoms or new cancer-related complications), or radiologic progression (on CT scan: $\geq 20\%$ enlargement in sum diameter of soft-tissue target lesions [RECIST 1.1 criteria]; on bone scan: ≥ 1 new bone lesions), initiation of ADT or death due to any cause, whichever occurs first. Death is considered a severe adverse event here.

Progression Free Survival (PFS) is defined as the time from starting treatment to the time of progression as defined above. Subjects who do not progress will be censored at the time of the last contact.

ADT Free Survival (ADT-FS) is defined as the time from starting treatment to the time of initiation of palliative ADT. ADT will typically be initiated on tumor progression and/or development of new metastases. Subjects who do not start ADT will be censored at the time of the last contact.

Time to Progression (TTP) is defined as the time from starting treatment to the time of first documented tumor progression or new lesions by CT and/or bone scan or initiation of ADT. Subjects who do not progress will be censored at the time of the last contact. In addition, death from any cause will also be censored.

Time to New Metastasis (TNM) is defined as the time from starting treatment to the time of a new documented tumor metastasis by CT and/or bone scan. Subjects who do not progress will be censored at the time of the last contact.

Overall Survival (OS) is defined as the time from starting treatment until death due to any cause. For subjects who do not die, time to death will be censored at the time of last contact.

Locoregional Control (LRC) is defined as the time from starting treatment until local and/or regional relapse is documented

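### Time to new metastasis counts any site, but scheduled follow-up CT/MRI is worded as covering only the known sites, so new soft-tissue spread is not systematically looked for

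*Combined protocol and SAP*

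**What the plan says.** The endpoint is open to any site. Section 9.5.5 defines TNM as "the time from starting treatment to the time of a new documented tumor metastasis by CT and/or bone scan".

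The scheduled imaging is worded more narrowly. Section 6.7.2 has: "Bone scan and CT/MRI of metastatic site(s) will be at 6- and 12-months for all patients". The synopsis (Procedures) lists "CT/MRI Scan and Bone Scan or Axumin/Choline-PET of Involved Site at 6 months". Both study calendars in section 8 attach the same involved-site label to the CT/MRI row, while bone scan has its own row with no site limit.

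Other imaging is possible. Section 6.7.2 allows more scans where prompted ("unless indicated more frequently by clinical or laboratory findings"). PyL PET/CT is acquired from mid-thigh to skull, but only at participating sites (section 6.4). The calendar footnotes let other PET tracers stand in for CT/MRI. After month 12, section 6.7.1 leaves imaging to the treating physician.

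On the drug, section 4.4 states: "Radium-223 is an alpha-emitting radioisotope which is a bone-seeking calcium mimetic".

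**The concern.** The definition and the schedule do not match. A man with a single femoral lesion, followed by bone scan and CT of that site, meets the schedule without any required CT of pelvis, abdomen or chest. A new node or visceral lesion there counts towards TNM only if something else finds it. Until then he contributes metastasis-free time.

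This matters because the gap is not neutral between arms. If radium-223 delays new bone lesions and does little elsewhere, soft-tissue lesions form a larger share of new metastases in the radium arm than in the control arm. Missing them would then flatter the radium arm in TNM. The same would hold for time to distant progression if it counts the same lesions; section 9.5.5 gives no definition of it. Masked reading (section 9.1) cannot correct for anatomy that was not scanned.

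**Working it through.** **1. The texts side by side.**
- The involved-site or metastatic-site wording for CT/MRI stands in the synopsis, section 6.7.2 and both calendars. No section names a chest, abdomen or pelvis field at follow-up.
- Section 9.4 asks for the same method and technique over time, but for lesions already identified and reported. It does not define where to search for new ones.
- The two progression rules differ. In 9.5.1, progressive disease is a 20% increase in the sum of longest diameters, "taking as reference the smallest sum LD recorded since the treatment started or the appearance of" one or more new lesions, in any tissue. In 9.5.5, the CT component is "enlargement in sum diameter of soft-tissue target lesions", and new lesions are named only for bone scan.
- TNM names CT and bone scan. Whether a lesion seen only on PET counts is not stated.
- The calendars differ by arm. The SABR-arm imaging footnote lists DCFPyL among the PET alternatives and the radium-arm footnote does not. The later PSMA PET is timed from the second scan in one arm and from the first in the other. These may be drafting slips.

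**2. The plan's own figure, as a yardstick.** The plan gives no figure for TNM. For PFS, section 14.2 gives 30 per arm, hazard ratio (HR) 0.5, one-sided 0.1, 80% power, 18 months' accrual and 12 months' further follow-up.
- Events (Schoenfeld): 4 × (1.2816 + 0.8416)² / (ln 0.5)² = 37.5, so 38.
- Event probability with exponential PFS and uniform accrual: 0.751 control, 0.509 radium, mean 0.630.
- 38 / 0.630 = 60.3 patients. Sixty patients give 37.8 events and power 0.802. The design figure is reproduced.

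**3. Illustration for TNM.** Assumptions not in the documents: HR 0.5 for new bone lesions, HR 1.0 elsewhere, proportional and independent hazards. Let *s* be the control-arm share of new metastases outside bone and *c* the fraction of those that is found.
- Complete detection: HR = 0.5(1 − s) + s.
- Partial detection: HR = [0.5(1 − s) + s·c] / [(1 − s) + s·c].
- Section 4.5 puts bone above 90%, so *s* is at most about 10%.

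| s | all found | half found | none found |
|---|---|---|---|
| 5% | 0.525 | 0.513 | 0.50 |
| 10% | 0.55 | 0.526 | 0.50 |

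At s = 10%, non-bone lesions are 0.10 / 0.55 = 18% of new metastases in the radium arm, against 10% in the control arm.

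**4. The same in medians.** Section 14.5 plans Kaplan-Meier summaries and medians for TNM. With exponential times and s = 10%, missing every non-bone lesion lengthens the control median by 1 / 0.90 = 1.11 and the radium median by 0.55 / 0.45 = 1.22. The ratio of medians moves from 1 / 0.55 = 1.82 to 2.0.

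**5. Against sampling error.** The shift is ln(0.55 / 0.50) = 0.095 on the log scale. With 38 events the standard error of the log HR is about 2 / √38 = 0.32, so the shift is about 0.3 standard errors. The number of TNM events is not given.

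**The case against.** The strongest reply is that the site label is loose. Section 6.7.2 attaches the same words to PyL PET/CT, which section 6.4 acquires from mid-thigh to skull. The calendar row also carries the entry scan, used to count lesions and exclude lung and liver disease. Section 9.1, the last paragraph of 6.7.2 and the calendar footnotes carry no site limit. So the text may leave the CT field unspecified rather than restrict it. That much stands, but it does not close the gap: a centre that scans only the involved site complies with the plan.

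A reader might infer that new nodal or visceral lesions cannot be scored at all. The documents do not support that. Triggered scans, alternative PET, the CT part of PyL PET/CT (read for soft tissue at month 6) and lesions within the field of a regional CT are all routes to detection. The supportable statement is that such lesions are not systematically looked for.

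A reader might also infer a large bias by taking 30% or 50% of new lesions to lie outside bone. Those shares have no source. On the documents' only figure, 10% is a ceiling. That figure describes men with rising PSA after primary treatment, not new lesions after SABR, so it is only a rough guide.

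Finally, TNM is secondary and section 14.5 plans neither a hazard ratio nor a test for it. That limits the consequence, but the medians will still be read as covering any site.

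**Conclusion.** The mismatch is real and worth correcting. As written, TNM covers any site while scheduled conventional CT/MRI need cover only known sites, and detection elsewhere depends on centre, modality and triggers. If radium-223 acts mainly on bone, the bias favours the radium arm. Under HR 0.5 in bone, 1.0 elsewhere and at most about 10% non-bone disease, the extreme case of finding no non-bone lesion moves the TNM hazard ratio from at most 0.55 to 0.50. Any partial detection makes the shift smaller.

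It would be wrong to infer that the primary comparison is undermined. PFS in 9.5.5 also counts PSA rise, symptoms, ADT start and death, so missed soft-tissue spread has other ways to register. The weakness lies in TNM and, by inference, in time to distant progression.

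**What to change.** - Keep TNM, and report it in two parts: new bone metastasis on bone scan, which is systematically imaged, and new soft-tissue metastasis, described by arm and imaging modality.
- Do not claim an effect on new metastasis at any site from site-limited CT.
- State whether a lesion seen only on PET counts.
- Reconcile the new-lesion rule in 9.5.1 with that in 9.5.5.
- Where CT or PET/CT is already scheduled, use the same field as at baseline in both arms, and align the imaging footnotes of the two calendars.

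Replacing TNM with a bone-only endpoint is less attractive: it would discard soft-tissue events that are found and leave only the lesions radium-223 targets. Requiring chest, abdomen and pelvis CT in every man would add a procedure where MRI or PET is used. The changes above need no new scan type. They cost a narrower claim and slightly more reporting work; keeping the baseline field may widen some scheduled scans.
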